The risk of non-response to tianeptine during the study period is addressed by having close clinical follow up of study subjects and stringent withdrawal criteria. These criteria are (1) participant withdraws his or her consent; (2) significant clinical worsening in the judgment of the study clinician; (3) a CGI-Improvement rating⁷ by the study clinician of 6 (worse) or 7 (much worse) for 2 consecutive visits; or (4) development of significant side effects or an adverse event grade 3 or higher. Any subject meeting any of these criteria will be withdrawn from the study and treated clinically. Furthermore, subjects may be withdrawn if they repeatedly miss scheduled appointments. If clinical worsening necessitates more intensive treatment, appropriate clinical care will be given but if possible the patient will still complete the ongoing assessments and final imaging visits.

Should a subject express suicidal ideation at any time during a study visit, the study clinician will be contacted immediately to assess the subject and to determine the appropriate course of action. Options for addressing suicidal ideation will include contacting the individual's mental health caregiver (if available), referring for urgent (same day) evaluation and treatment in an outpatient clinic, or emergency room evaluation and hospitalization. Similar practices will be used for other emergencies, including but not limited to psychosis, homicidal or violent thoughts, or an acute change in a subject's physical status.

2.8. Tianeptine taper and post-protocol treatment.

Once all study assessments are completed, subjects will be tapered off of tianeptine medication. Subjects will have their dosage reduced to 12.5 mg twice daily for two weeks, then 12.5 mg once daily for two weeks, and then tianeptine will be discontinued. Subjects will be assessed every two weeks in this post-protocol phase, with continuation of HRSD and CGI rating

scales. Appropriate clinical options will be discussed with any subject demonstrating worsening HRSD (≥ 16 on 24-item scale) or CGI (Improvement score ≥ 5 or Severity score ≥ 4 for two consecutive weeks) scores, most likely including initiation of FDA-approved antidepressant medication.

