3.2 Exclusion Criteria

- 1) Any history of opioid-use disorder

- 2) Any history of moderate- non-opioid (except for Nicotine) substance-use disorder.
- 3) Any severity of alcohol use disorder (including mild)
- 4) Past or current psychosis, psychotic disorder (including psychotic MDD), mania, or bipolar disorder
- 5) Hamilton Rating Scale for Depression (HRSD) suicide item > 2 or Clinical Global Impressions (CGI)-Severity score of 7 at baseline
- 6) Previous or current treatment with Tianeptine
- 7) Current treatment or currently taking an opioid.
- 8) Failed depression treatment with electroconvulsive therapy.
- 9) Acute, severe, or unstable medical illness
- 10) Weight > 300 lbs, or girth size incompatible with scanner bore.
- 11) Any physical or intellectual disability adversely affecting ability to complete assessments. MMSE <26
- 12) for MSSM site - Having contraindication to MRI scanning (such as metal in body) or inability to tolerate the scanning procedures (e.g., severe obesity, claustrophobia)
- 13) Current pregnancy or currently breast feeding.
- 14) Abnormal baseline liver function tests
- 15) Currently being treated with an antidepressant medication, an antipsychotic or mood stabilizer.
 - a) If a participant is taking a protocol dis-allowed medication at the time of screening and despite medication treatment still meets the inclusion criteria of an HRSD>16, the participant may discontinue the medication under the supervision of their treating physician or the study clinician.
- 16) Positive urine toxicity at screening (except for cannabinoid)

4. Primary Study Endpoints

- 1. HRSD change from Week 0 to Week 8

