4.1 Secondary Study Endpoints

- 1. Response rate to tianeptine (baseline HRSD decreases by $\geq 50\%$)
- 2. Remission rate to tianeptine (final HRSD ≤ 7)
- 3. Change in VAS pain scores from Week 0 to Week 8
- 4. Change in emotional pain as measured by the ARSQ from Week 0 to Week 8

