5.2 Statistical Methods

Descriptive analyses for all variables collected at all time points will be conducted both overall and by study site. If differences are found between the study sites on outcomes of interest, then study site will be adjusted for in the analyses. For the intent-to-treat sample (i.e. those who started on drug at week 1 regardless of compliance across the 8 weeks), we will report proportions of responders and remitters and mean changes in HRSD, VAS pain score, and ARSQ from week 0 to week 8. In addition to these point estimates, we will report the corresponding 95% confidence intervals. Similar analyses will be done on the sample of completers (i.e. those who complied with drug administration across all 8 weeks based on pill counts of at least 80%).

To examine the hypothesis that baseline pain level will be predictive of response to tianeptine, we will further investigate whether any single baseline pain battery score can be used to construct subgroups of subjects showing greater response to tianeptine. Based on the distribution of a given pain battery score and preliminary exploratory bivariate modelling, we will dichotomize the pain score (low/high) and compare response/remission rates and change scores for HRSD between the groups corresponding to low and high pain battery score. We will

report effect sizes corresponding to differences in response/remission rates and differences in HRSD change scores. Exploratory analyses will employ multivariable logistic (for response/remission outcomes) and linear (for HRSD change score) regression to investigate whether combinations of baseline pain scores can be used to identify subgroups who will show greater response to tianeptine. Additional analyses will employ multivariable logistic and linear regression to investigate associations between baseline neuropsychiatric and/or MRI measures and remission/response or HRSD change score. To take advantage of the fact that HRSD and TESS are collected at each study visit (8 post-baseline measures), we will also employ linear mixed effects models to investigate the effects of each baseline pain battery score on HRSD and TESS over time.

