Unexpected adverse event or *unexpected suspected adverse reaction*. An adverse event or suspected adverse reaction is considered "unexpected" if it is not listed in the investigator brochure or is not listed at the specificity or severity that has been observed; or, if an investigator brochure is not required or available, is not consistent with the risk information described in the general investigational plan or elsewhere in the current application, as amended. For example, under this definition, hepatic necrosis would be unexpected (by virtue of greater severity) if the investigator brochure referred only to elevated hepatic enzymes or hepatitis. Similarly, cerebral thromboembolism and cerebral vasculitis would be unexpected (by virtue of greater specificity) if the investigator brochure listed only cerebral vascular accidents. "Unexpected," as used in this definition, also refers to adverse events or suspected adverse reactions that are mentioned in the investigator brochure as occurring with a class of drugs or as anticipated from the pharmacological properties of the drug, but are not specifically mentioned as occurring with the particular drug under investigation.

Adverse Event Reporting Period: The study period during which adverse events must be reported is normally defined as the period from the initiation of any study procedures to the end of the study treatment followup. For this study, the study drug follow-up is defined as 24 hours following the last administration of study drug (or the end of the study for those who must stop tianeptine but continue with the assessments).

Preexisting Condition: A preexisting condition is one that is present at the start of the study. A preexisting condition will be recorded as an adverse event if the frequency, intensity, or the character of the condition worsens during the study period.

General Physical Examination Findings: At screening, any clinically significant abnormality will be documented. At the end of the study, any new clinically significant findings/abnormalities that meet the definition of an adverse event will also be recorded and documented as an adverse event.

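### A week-8 HRSD score obtained after rescue treatment can be counted as response to tianeptine, because the plan has no rule for such scores

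*Combined protocol and SAP*

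**What the plan says.** Section 2.7 lists the withdrawal criteria, which include significant clinical worsening, and states: "Any subject meeting any of these criteria will be withdrawn from the study and treated clinically". Two sentences later it says: "If clinical worsening necessitates more intensive treatment, appropriate clinical care will be given but if possible the patient will still complete the ongoing assessments", and it extends this to the final imaging visits. Section 6.1, in defining the adverse event reporting period, makes separate provision for "those who must stop tianeptine but continue with the assessments".

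The primary endpoint in Section 4 is "HRSD change from Week 0 to Week 8". The first secondary endpoint in Section 4.1 is labelled "Response rate to tianeptine" and requires only a fall of at least half from baseline HRSD. Remission requires only a final HRSD of 7 or less. Neither definition mentions whether the patient is still on tianeptine or has started anything else.

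Section 5.2 defines the intent-to-treat set as "those who started on drug at week 1 regardless of compliance across the 8 weeks" and says of it: "we will report proportions of responders and remitters and mean changes in HRSD, VAS pain score, and ARSQ from week 0 to week 8". I read the set as everyone who took drug, since Section 2.5 starts tianeptine at Week 0. The same analyses are repeated in completers, defined by a pill count of at least 80%. Section 2.6 prohibits other antidepressants during the study. No section says how an HRSD score taken after such a drug is started is to be analysed.

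**The concern.** Take a patient who worsens on tianeptine, is moved to other treatment, and remains under assessment as Section 2.7 allows. The HRSD is scheduled weekly to week 8, so this patient can have an observed week-8 score. Nothing in Sections 4, 4.1 or 5.2 removes that score or conditions it on treatment. If it is low enough, the patient is a responder to tianeptine, and the improvement enters the primary mean change in any case.

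In a two-arm trial, rescue in the control arm would offset some of this. Here there is one arm, so any benefit of rescue is credited to tianeptine. The comparison of low-pain and high-pain groups is affected too if rescue is more common in one of them. The question concerns scores that are observed. It is separate from how missing week-8 scores are handled.

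**Working it through.** **The plan's own figures.** Section 5.1 gives no figure for rescue. Its design figures, with N = 75, groups of 37 and 38, and a two-sided 5% test, do reproduce:
- 10% against 40%: the pooled rate is (3.7 + 15.2)/75 = 0.252. The null SE is √(0.252 × 0.748 × (1/37 + 1/38)) = 0.1003. The alternative SE is √(0.09/37 + 0.24/38) = 0.0935. Power is Φ((0.30 − 1.96 × 0.1003)/0.0935) = Φ(1.106) = 86.6%, against 86% stated.
- d = 0.33: Φ(0.33 × √75 − 1.96) = 81.5% (80.5% by noncentral t), against more than 80% stated.
- Widest 95% interval for a rate: 2 × 1.96 × √(0.25/75) = 22.6 points, against at most 25 stated.

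None of these is in dispute.

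**Path of a rescued patient through the plan.**
1. Still assessed after rescue? Section 2.7 says withdrawn, then says assessed if possible. Section 6.1 confirms that some patients are assessed off drug.
2. In the intent-to-treat set? Yes; the only condition in Section 5.2 is having started drug.
3. Week-8 score used? Section 5.2 uses week-8 change and states no exception.
4. Counted as a responder or remitter? Section 4.1 looks only at the HRSD.

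**Size.** The documents give no rescue rate, so the following inputs are assumptions: f is the share rescued and still assessed at week 8, r is the share of those meeting the response rule, and g is the HRSD gain attributable to rescue. The denominator is taken as 75.

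One rescued responder adds 1/75 = 1.3 points to the response rate. Within a pain group it adds 1/38 = 2.6 or 1/37 = 2.7 points.

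Overstatement of the response rate = 100 × f × r. Shift in mean HRSD change = f × g.

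| f | r = 20% | r = 50% | g = 4 | g = 12 |
|---|---|---|---|---|
| 5% | 1.0 points | 2.5 points | 0.2 HRSD | 0.6 HRSD |
| 10% | 2.0 points | 5.0 points | 0.4 HRSD | 1.2 HRSD |
| 20% | 4.0 points | 10.0 points | 0.8 HRSD | 2.4 HRSD |

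An example in whole patients: 8 of 75 are rescued and 4 of them respond, and 27 of the other 67 respond. As planned, the rate is 31/75 = 41.3% (Wilson 95% interval 30.9 to 52.6). With rescue counted as non-response it is 27/75 = 36.0% (26.1 to 47.3). The difference is 4/75 = 5.3 points.

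**What the completer set does.** A patient who leaves tianeptine at week 3 has 3/8 = 37.5% exposure and is excluded. Reaching 80% takes 0.8 × 8 = 6.4 weeks, which leaves at most 1.6 weeks on rescue before week 8. So most rescued patients drop out of that analysis. They leave the denominator as well as the numerator, so they are not counted as failures, and the intent-to-treat result is unchanged.

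**The case against.** The strongest reply is that Section 2.7 withdraws patients who worsen and that continued assessment is only hoped for. This stands in part. A reader might infer that every rescued patient stays to week 8 and is counted. The documents do not say that. Inclusion is the default reading of an intent-to-treat, week-8 analysis with no exclusion rule, not an instruction. But nothing says that withdrawn patients leave the analysis set, and Section 6.1 shows that some go on being assessed.

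A second reply is that analysing everyone who started drug is a deliberate and respectable choice, and that a single-arm change already contains natural course and regression to the mean. That is fair. Keeping these patients and collecting their later scores is good practice. The gap is that improvement on another treatment can appear under an endpoint named for tianeptine.

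Third, the effect may be small. Under Section 3.1 these patients have at least two failed treatments in the current episode. They have then worsened, and must still fall by half from baseline in the weeks that remain. What counts as more intensive treatment is also undefined. This stands for the response rate, although any gain on rescue moves the mean change.

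Two further readings are tempting and unsupported. One is that post-rescue scans will be analysed as tianeptine scans. The documents schedule a post-treatment MRI but define no pre/post comparison into which it would go. The other is that the planned mixed model already handles the problem. Section 5.2 plans it only for the effects of baseline pain scores over time, not for the primary mean change.

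**Conclusion.** The point holds as a gap in the plan. Sections 2.7 and 6.1 must be reconciled on whether, and in what sense, a patient who worsens remains in the study. As the text stands, an observed score after rescue can be credited to tianeptine in the response rate, the remission rate and the primary mean change. The completer analysis reduces the exposure without correcting the main result.

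The size cannot be known from the documents. Under the assumed ranges it is about 1 to 10 points on the response rate, probably near the low end, and about 0.2 to 2.4 points on the mean HRSD change. The sample size and stated power are unaffected. It should be settled before analysis, because a rule chosen after seeing the scores would be open to question.

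**What to change.** - Reconcile the two statements in Section 2.7 with Section 6.1, and state what withdrawal means for the week-8 analysis.
- In Sections 4.1 and 5.2, count any patient who starts another antidepressant treatment, or more intensive care for worsening, before week 8 as a non-responder and non-remitter, and keep that patient in the denominator.
- For HRSD change, keep the estimate from all observed scores and add a sensitivity estimate that sets aside scores taken after rescue, using the weekly HRSD already collected. State it as a new analysis with its missing-data assumption. Such an estimate describes the course these patients would have had without rescue, which the data cannot verify.
- Record the rescue start date; the clinical and medication progress note is already scheduled at every visit. Report the number rescued, overall and by pain group, and flag post-rescue MRI scans.

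The cost is a few sentences, one date field and one extra analysis. The downside is a slightly lower stated response rate. Clinical care does not change.

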3.1 Inclusion Criteria

- 1) Age 21 – 60 years, male or female
- 2) Current diagnosis of Major Depressive Disorder (MDD) without psychotic features
- 3) 24-item Hamilton Rating Scale for Depression (HRSD) ≥ 16
- 4) At least two previous antidepressant treatment failures (adequate trials within current episode) with a SSRI, SNRI, bupropion, tricyclic antidepressant, mirtazapine, nefazodone, or monoamine oxidase inhibitor, or transcranial magnetic stimulation (TMS), or IV ketamine or nasal ketamine.
- 5) Capable of providing informed consent and complying with study procedures
- 6) Currently using or willing to use contraception, if woman of childbearing potential (such as condoms, IUD, or oral contraceptive), for duration of the study.

3.2 Exclusion Criteria

- 1) Any history of opioid-use disorder

- 2) Any history of moderate- non-opioid (except for Nicotine) substance-use disorder.
- 3) Any severity of alcohol use disorder (including mild)
- 4) Past or current psychosis, psychotic disorder (including psychotic MDD), mania, or bipolar disorder
- 5) Hamilton Rating Scale for Depression (HRSD) suicide item > 2 or Clinical Global Impressions (CGI)-Severity score of 7 at baseline
- 6) Previous or current treatment with Tianeptine
- 7) Current treatment or currently taking an opioid.
- 8) Failed depression treatment with electroconvulsive therapy.
- 9) Acute, severe, or unstable medical illness
- 10) Weight > 300 lbs, or girth size incompatible with scanner bore.
- 11) Any physical or intellectual disability adversely affecting ability to complete assessments. MMSE <26
- 12) for MSSM site - Having contraindication to MRI scanning (such as metal in body) or inability to tolerate the scanning procedures (e.g., severe obesity, claustrophobia)
- 13) Current pregnancy or currently breast feeding.
- 14) Abnormal baseline liver function tests
- 15) Currently being treated with an antidepressant medication, an antipsychotic or mood stabilizer.
 - a) If a participant is taking a protocol dis-allowed medication at the time of screening and despite medication treatment still meets the inclusion criteria of an HRSD>16, the participant may discontinue the medication under the supervision of their treating physician or the study clinician.
- 16) Positive urine toxicity at screening (except for cannabinoid)

4. Primary Study Endpoints

- 1. HRSD change from Week 0 to Week 8

4.1 Secondary Study Endpoints

- 1. Response rate to tianeptine (baseline HRSD decreases by $\geq 50\%$)
- 2. Remission rate to tianeptine (final HRSD ≤ 7)
- 3. Change in VAS pain scores from Week 0 to Week 8
- 4. Change in emotional pain as measured by the ARSQ from Week 0 to Week 8

4.2 Primary Safety Endpoints

The primary safety endpoint is:

Rate of serious adverse events (SAEs):

All SAEs will be assessed by a study physician to determine whether the relationship to the study procedures or treatment is considered to be likely, unlikely or unknown.

5. Statistical Plan

5.1 Sample Size Determination

With total sample size of 75 subjects, we have >80% power to detect an effect size for a change in HRSD (from week 0 to week 8) of at least (Cohen's) $d = 0.33$ (small-medium), using a 2-sided test with a 5% significance level. With this sample size we can construct 95% confidence intervals for the response/remission rates that are no more than 25 percentage points wide. For our subgroup analyses to examine the hypothesis that baseline pain (physical or emotional) will differentially relate to improvement in depression, assuming a median split (low/high, $n = 37/38$) for a given physical or emotional pain battery score, we have >80% power to detect an effect size for a difference in change in HRSD (low group vs. high group) of at least $d = 0.66$ (medium-large), using a 2-sided test with a 5% significance level. Similarly, we have >80% power to detect differences in proportions of responders/remitters between the pain groups that are at least 30 percentage points. As an example, if depression response/remission is 10% in the low pain group and 40% in the high pain group, we have 86% power to find this statistically significant at the 5% significance level.

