We have chosen to recruit subjects and perform all assessments except for neuroimaging procedures at the two sites (N=24 at each site for overall study N=75, 28 already entered), which will increase the rate of participant enrollment, ensure that recruitment goals are met, and enhance the generalizability of the sample. Structural and task-based magnetic resonance imaging (MRI) will be performed solely under [name] direction at NYSPI in order to maintain internal validity of the data set. MSSM subjects will be transported to NYSPI to complete neuroimaging procedures as described below.

2.2. Subject recruitment and screening procedures.

Recruitment will proceed in parallel at each study site by means of (1) screening individuals who directly contact the clinical programs at MSSM and SUSM, (2) referral from clinicians in other disciplines at the component institutions participating in this project, and (3) outreach to the communities surrounding MSSM and SUSM. We also promote recruitment of under represented minority subjects by anticipating and working to eliminate barriers to research participation. Promotional materials at each component clinic allay these concerns by explaining how our studies are designed to mitigate and overcome these barriers to participation in research studies.

Potential subjects will be evaluated by remote and/or in-person meetings. Those who decide to participate by signing informed consent will have an evaluation inclusive of a clinical interview by a study clinician, structured diagnostic interview, and completion of standardized rating scales (trained rater) in order to document eligibility. Eligible subjects will have further documentation of vital signs, medical history urine drug screen, CBC, chemistries and electrolytes, thyroid profile, urine analysis, standing/supine systolic/diastolic BP, and ECG. Female participants will undergo urine pregnancy testing to confirm that they are not pregnant prior to drug initiation and will be instructed to use effective birth control during the study, such as condoms, IUDs, oral contraceptives, or depot contraceptives. Participants also will be scheduled for further baseline testing as described below.

2.3. Imaging procedures.

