Following screening and baseline testing, all subjects will begin tianeptine 12.5 mg three times daily (total daily dose 37.5 mg/day) for a total duration of 8 weeks of treatment. Subjects who develop side effects that prevent them from taking the full three times daily dosage will have their dosage reduced to tianeptine 12.5 mg twice daily, and those unable to tolerate at least 25 mg/day dosing will be dropped out of the study. Based on the extensive experience of clinicians in Europe, where tianeptine is approved for the treatment of depression, we expect this dosage regime to be well-tolerated. During the study, concomitant use of other antidepressants, antipsychotics, anticonvulsants, central nervous system stimulants, anti-addiction agents, and cognitive enhancers are prohibited, with the exception of small doses of benzodiazepines (≤ 2 mg lorazepam equivalents per day), which will be permitted for anxiety or insomnia.

Medication was purchased from Neuraxpharm in Germany and shipped to the NYSPI pharmacy where it is stored. Medication is shipped to the MSSM pharmacy, where it is packaged and prescribed for MSSSM patients in containers containing a 2 week supply (50 blister packed 12.5 mg pills – enough for two weeks plus an additional pills alloatted in case of a delayed visit) at the 0, 2,4, and 6 week visits and 20 blister packed pills for the final taper. Medication is shipped to the Stanford Depression Research Clinic in the same quantities and it is dispensed to patients using the same procedures as atMSSM. At each in person visit, the subject should return the bottle, and the number of remaining pills will be counted and recorded to monitor compliance.

2.7. Early discontinuation criteria and handling of emergencies.

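### The power stated for HRSD change in section 5.1 assumes that all 75 entered patients have a Week 8 HRSD; at an assumed 5 to 20% loss it is about 78 to 71%, not above 80%

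*Combined protocol and SAP*

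**What the plan says.** Section 4 makes HRSD change from Week 0 to Week 8 the primary endpoint. Section 5.1 opens: "With total sample size of 75 subjects, we have >80% power to detect an effect size for a change in HRSD" and gives the effect as "of at least (Cohen's) $d = 0.33$ (small-medium), using a 2-sided test with a 5% significance level". For the pain hypothesis it proceeds "assuming a median split (low/high, $n = 37/38$) for a given physical or emotional pain battery score" and claims the same power, where the target is now the "difference in change in HRSD (low group vs. high group) of at least $d = 0.66$ (medium-large), using a 2-sided test with a 5% significance level". The two groups add to 75.

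Section 2.1 gives the recruitment figure as "N=24 at each site for overall study N=75, 28 already entered", so 75 counts patients entered. (Two sites of 24 plus 28 make 76; the difference of one does not affect this point.)

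Other sections foresee loss. In section 2.6, "those unable to tolerate at least 25 mg/day dosing will be dropped out of the study". In section 2.7, after four withdrawal criteria, "Any subject meeting any of these criteria will be withdrawn from the study and treated clinically"; repeated missed appointments may also lead to withdrawal. The DSMB text provides for monitoring of drop-outs.

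Two provisions work the other way. Section 2.7 adds that patients whose worsening needs more intensive treatment should, where possible, still finish the assessments. The definition of the adverse event reporting period in section 6.1 recognises patients who stop tianeptine but stay in assessment.

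Section 5.2 defines the intent-to-treat sample by drug start, whatever the later compliance. It states no rule for a missing Week 8 HRSD. Nowhere do the documents give a dropout rate, an inflation of the sample size or an expected evaluable number.

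**The concern.** A change score from Week 0 to Week 8 needs a Week 8 value. Section 5.1 assumes that nobody lacks one, while sections 2.6 and 2.7 describe how patients leave early. The stated effects are also almost exactly the smallest that 75 patients can detect at 80% power, so there is little reserve to absorb any loss.

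What is at stake is how the results are read, above all a null result in the comparison of low and high pain groups, which addresses the study's central hypothesis. Such a result would be judged against a stated power above 80% that the comparison would not have had.

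**Working it through.** **Inputs.** From section 5.1: n = 75, split 37/38; d = 0.33 and d = 0.66; two-sided 5%. Assumed, because the documents give no rate: 5, 10, 15 or 20% of patients without a Week 8 HRSD. These leave 71, 67, 64 or 60 patients (75 × 0.95 = 71.25; × 0.90 = 67.5, rounded down; × 0.85 = 63.75, rounded up; × 0.80 = 60). Patients without a Week 8 value are taken to drop out of the change score, since section 5.2 offers nothing else for it.

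**Method.** Section 5.1 names no test. I used t-test power from the noncentral t distribution:
- one-sample (change from zero): df = n − 1, noncentrality = d√n;
- two-sample (low versus high pain): df = n₁ + n₂ − 2, noncentrality = d√(n₁n₂/(n₁ + n₂)).

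Power is the probability that |t| exceeds the two-sided 5% critical value.

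**Step 1: the plan's own figures.**
- Overall: 0.33 × √75 = 2.858, critical value 1.993 on 74 df; power 80.5%.
- Pain groups: 0.66 × √(37 × 38/75) = 2.858, critical value 1.993 on 73 df; power 80.5%.

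Both claims reproduce. The effects detectable at exactly 80% power with 75 patients are 0.328 and 0.656, which round to the plan's 0.33 and 0.66. The normal approximation gives about 0.32 and 0.65, so t-tests were very probably used.

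**Step 2: power with Week 8 values missing.**

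| Assumed loss | With Week 8 HRSD | Power, d = 0.33 overall | Split | Power, d = 0.66 between groups |
|---|---|---|---|---|
| 0% | 75 | 80.5% | 37/38 | 80.5% |
| 5% | 71 | 78.3% | 35/36 | 78.3% |
| 10% | 67 | 75.9% | 33/34 | 75.8% |
| 15% | 64 | 73.9% | 32/32 | 73.9% |
| 20% | 60 | 71.0% | 30/30 | 71.0% |

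Under the normal approximation the figures are about one point higher: 81.5% at 75, 77.1% at 67, 75.2% at 64 and 72.5% at 60.

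**Step 3: effects that the reduced numbers support.** At 64 patients the effects detectable at 80% power are 0.356 overall and 0.711 between groups of 32. To two decimals, with power above 80%, these become d = 0.36 (80.9%) and d = 0.72 (80.9%). Rounding the second down to 0.71 would give 79.8%.

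**Step 4: the other statements in section 5.1.**
- 10% versus 40% responders or remitters: 86.6% at 37/38 by the pooled normal formula (the plan says 86%), and still 80.6% at 32/32.
- 95% confidence interval no wider than 25 points: the largest exact (Clopper-Pearson) width is 23.6 points at 75, 24.9 at 67 and 25.1 at 66. The Wald width, 2 × 1.96 × √(0.25/n), is 22.6 points at 75, 24.9 at 62 and 25.1 at 61.

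**The case against.** The strongest objection is that stopping treatment does not mean lacking a Week 8 HRSD. Section 2.7 asks for assessments to continue where possible after worsening, section 6.1 allows for patients who stop drug but stay in assessment, and the intent-to-treat sample ignores compliance. This stands in part: actual loss may be smaller than the withdrawal rules suggest. But the section 2.7 provision covers one route out and is conditional, and none of these passages supplies a value for a patient who is not seen at Week 8.

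A second objection is that section 5.2 plans mixed models over all post-baseline visits, which can use patients without a Week 8 value. Those models concern the effects of baseline pain scores over time. They may soften the loss for the pain question, but they are not the change-score comparisons that section 5.1 powers.

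Third, the consequence is modest. The study has one arm, section 5.2 reports the primary change as a mean with a confidence interval, and a pre-post effect of 0.5 would have 97% power even with 60 patients. That is fair, and it is why the remedy is limited to restating section 5.1.

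Three stronger readings are tempting, and the documents do not support them:
- *A single missing patient defeats both claims.* At 74 patients t-test power is 79.99% and 79.98%, which is 80% for any practical purpose. By the normal approximation, which the plan does not exclude, it is 81.0%, and the minimum is 73.
- *Every figure in section 5.1 is at its limit.* Step 4 shows that the responder example and the interval width have room.
- *The pain-group comparison suffers most.* Its loss of power is practically identical to that of the overall comparison.

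Nor does the planned completer analysis show missing data: completers are defined by pill count, not by having a Week 8 HRSD.

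**Conclusion.** The concern holds for the two HRSD-change claims. Power above 80% for d = 0.33 overall and d = 0.66 between pain groups is correct only if practically all 75 entered patients have a Week 8 HRSD. At an assumed 5 to 20% loss, power for both is about 78 to 71%. This rests on t-tests, on loss rates that are illustrative, and on complete-case change scores, which is the only reading section 5.2 leaves open. The plan's arithmetic is right at 75; what is missing is any allowance for loss that its own text foresees.

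**What to change.** Keep 75 entered. Restate section 5.1 for the expected number with a Week 8 HRSD, and name the test used. Take the rate of missing Week 8 values from those of the 28 patients already entered who have reached Week 8. Show it with a range, because a rate from at most 28 patients is imprecise. If it were 15%, the text would say that 64 patients with a Week 8 HRSD give >80% power for d = 0.36 overall and d = 0.72 between pain groups of 32 each. State the number on which the confidence interval width is based, and the interval method.

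The cost is a change of wording and slightly less favourable detectable effects (0.33 to 0.36 and 0.66 to 0.72 in this example). No extra patients are needed.
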